**REACH Intervention:
Improving Medication Adherence Among Underserved Patients With Type 2 Diabetes**

NCT02409329

03/31/2020

NCT02409329 – Statistical Analysis plan

REACH treatment effects – any REACH vs. Control

All analyses were performed using R v.3.5.1. We employed multiple imputation with chained equations to address missing data ($m=1,000$ imputed datasets). Statistical significance for each hypothesis test was determined at the $\alpha=0.05$ level. All analyses compare those receiving the REACH intervention (i.e., REACH or REACH + FAMS) to control except for the subgroup analyses estimating additional effects of also receiving FAMS.

We used generalized estimating equations (GEE) with a working-exchangeable correlation structure and identity link (1), adjusting for baseline and allowing a time-treatment interaction. We adjusted for the baseline value of the outcome of interest with restricted cubic splines (three knots) to allow for a nonlinear effect of the baseline value. For each outcome, we performed an omnibus test of the treatment effect using a robust variance-covariance based Wald statistic. We used ordinary least squares linear regression with Huber-White heteroscedasticity-consistent standard errors (2) to obtain point estimates and 95% CIs for the intervention effect on each outcome at each time point.

REACH only and REACH+FAMS vs. Control

Half of the intervention group received REACH only and the other half received REACH+FAMS for the first 6 months. Both intervention groups received REACH only during months 6-12. Data visualizations suggested effect modification by baseline HbA1c, in which those with a higher baseline HbA1c demonstrate a larger estimated effect at 3 and 6 months than those with a lower baseline HbA1c. To increase our power to detect any differential effects for REACH only as compared to REACH+FAMS, we conducted analyses with a subset of data including participants with a baseline HbA1c $\geq 8.5\%$ (69 mmol/mol; $n=219$), which was the approximate mean value for baseline HbA1c. With this reduced dataset, we conducted the same GEE model described above for REACH only vs. control and, separately for REACH+FAMS vs. control. We used ordinary least squares linear regression with Huber-White heteroscedasticity-consistent standard errors (2) to obtain point estimates and 95% CIs for the intervention effect on each outcome at each time point.

References:

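### Do the OLS models behind the reported estimates and 95% CIs carry the baseline adjustment described for the GEE?

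*SAP*

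**What the plan says.** The SAP is the only statistical text; the protocol has no analysis section. In the SAP section comparing any REACH with control, four statements follow one another:

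- The GEE is fitted "adjusting for baseline and allowing a time-treatment interaction".
- Then: "We adjusted for the baseline value of the outcome of interest with restricted cubic splines (three knots) to allow for a nonlinear effect". This sentence names no model.
- The GEE supplies the hypothesis test: "For each outcome, we performed an omnibus test of the treatment effect using a robust variance-covariance based Wald statistic".
- Estimation comes from a different model: "We used ordinary least squares linear regression with Huber-White heteroscedasticity-consistent standard errors (2) to obtain point estimates and 95% CIs", and these are given "for the intervention effect on each outcome at each time point".

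In the section on REACH only and REACH+FAMS, restricted to the 219 participants with baseline HbA1c of at least 8.5%, the SAP states that "we conducted the same GEE model described above for REACH only vs. control and, separately for REACH+FAMS vs. control". It then repeats the OLS sentence word for word, again with no covariates.

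**The concern.** Every effect size and interval comes from the OLS, yet its covariates are not listed. The spline sentence directly follows the GEE sentence, and the omnibus-test sentence separates it from the OLS sentence. A strict reader could therefore attach the spline to the GEE alone. In the second section, the explicit reference back is attached to the GEE only.

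If the OLS had no baseline term, the reported intervals would come from a less precise model than the one used for the test. Someone reproducing the results from the SAP would have to choose between an adjusted and an unadjusted fit, and the two can give intervals of clearly different width.

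**Working it through.** The documents state no power, SD, effect size or interval width, so there is no figure to reproduce. The check is a reading of the text, followed by an illustration of what each reading would imply.

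**1. The text.** The GEE sentence already says that baseline is adjusted for. The next sentence is free-standing: it describes adjustment for the baseline of the outcome of interest and is not confined to one model. The OLS sentence belongs to the same paragraph. The second section repeats that OLS sentence identically, which signals the same procedure and adds no second gap.

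**2. If the OLS carries the spline.** In a simulation of 1,500 trials per correlation (four visits, N = 525, equal groups), the GEE and OLS visit estimates differed by an SD of 0.003 outcome SDs and the SE ratio was 1.00. There is no consequence.

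**3. If the OLS has no baseline term.** Inputs:

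- N = 525, the accrual goal in the protocol's Subject Population(s) section. This is not the analysed number.
- Equal any-REACH and control groups (assumed; no allocation ratio to control is given).
- Outcome SD of 1 and baseline-outcome correlation rho of 0.3, 0.5 or 0.7 (assumed).

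Formulas:

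- Unadjusted half-width = 1.96 × 2/sqrt(525) = 0.171.
- Adjusted half-width = 0.171 × sqrt(1 − rho²).
- Width ratio = 1/sqrt(1 − rho²).
- Chance that the unadjusted CI excludes zero when the adjusted chance is 80% = Phi(2.802 × sqrt(1 − rho²) − 1.96).

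| rho | sqrt(1 − rho²) | Adjusted half-width | Width ratio | Unadjusted chance of excluding zero |
|---|---|---|---|---|
| 0.3 | 0.954 | 0.163 | 1.048 | 76% |
| 0.5 | 0.866 | 0.148 | 1.155 | 68% |
| 0.7 | 0.714 | 0.122 | 1.400 | 52% |

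The ratio hardly depends on allocation. With two thirds of participants in the intervention groups, simulated half-widths are about 0.181 unadjusted against 0.173, 0.157 and 0.130 adjusted, with ratios of 1.047, 1.153 and 1.397.

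**4. If the OLS has a linear baseline term.** Across the simulated settings (N = 525 and N = 219, straight and curved true relations), the half-width with a linear term divided by that with the spline ran from 0.997 to 1.043. The form of the adjustment therefore matters little. Only the choice between some adjustment and none has a visible effect.

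**5. The HbA1c subset.** Selecting on baseline changes the correlation within the subset. With a normal baseline, rho of 0.3, 0.5 and 0.7 becomes 0.19, 0.33 and 0.51, and the widening is about 2%, 6% and 16%. With a right-skewed baseline (assumed gamma from 6.8%), it is 4–5%, 14–16% and 37–42%. Baseline shape is not given, so the formula in step 3 with a range for rho is as much precision as the question deserves.

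**The case for a change.** The strongest case for acting is that the gap is real and cheap to close. Where the authors wanted something carried over they said so, and they said it of the GEE only. The spline sentence can fairly be read as an elaboration of the GEE clause before it. Guessing wrongly has visible effects: at an assumed true effect of 0.2 SD, the unadjusted and spline-adjusted fits gave different calls at the 5% level in about 9% to 31% of simulated trials.

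What stands is that the covariate list is not written down. The rest does not make it a defect. The differing calls arise only if the OLS contained no baseline term, and the SAP nowhere says or implies that. Separate models by visit are themselves an inference, since the SAP says only that estimates were obtained at each time point. Nor does the handling of missing data need restating for the OLS: multiple imputation is set out in the opening paragraph, before any model is introduced.

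An argument from mismatch between the omnibus test and the intervals does not help either. Some mismatch occurs with either model. In a normal approximation with four visits and an assumed between-visit correlation of 0.6, the test and the set of visit CIs disagreed, counting both directions, in 15.0%, 11.6% and 20.2% of trials with unadjusted OLS. With adjusted OLS the figures were 16.9%, 13.2% and 3.6% (rho 0.3, 0.5, 0.7). Unadjusted OLS is thus worse only at rho 0.7, and there the gap narrows to 22.7% against 18.7% if the between-visit correlation is 0.8.

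**Conclusion.** No change to the plan is needed. The SAP leaves out a covariate list that its own paragraph supplies on the ordinary reading: the OLS adjusts for the baseline of the outcome with the same three-knot spline as the GEE. On that reading nothing is lost.

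On the least favourable reading, randomisation keeps the estimates unbiased and the CIs valid. The cost is precision alone: intervals about 5%, 15% or 40% wider at rho 0.3, 0.5 or 0.7. A linear term in place of the spline would cost about 4% at most in the settings simulated. These sizes rest on assumed correlations, complete data and, for the half-widths, the accrual goal split equally; none is a trial result. The point is one of reporting detail and does not bear on the soundness of the analysis.

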Describe plans for assuring that any action resulting in a temporary or permanent suspension of a federally funded research project is reported to the grant program director responsible for the grant.

The PI and KSP will review our data each week. Any serious, unanticipated events will be promptly reported to the IRB and the grant program director (within 10 working days).

Describe plans for assuring data accuracy and protocol compliance.

The PI trains all research assistants on protocol compliance and about the process of informed consent, and checks for RAs' ability to comply with all protocols before enrolling any participants. The PI and KSP will ensure quality control by conducting regular data verification, reporting reviews, and protocol compliance checks. The PI will complete annual reports detailing the study progress.

Is Vanderbilt going to be the Coordinating Center?

Yes

No

Please select the phase of study.

Phase I

Phase I/II combined

Phase II

Phase III,

Phase IV

N/A

Does this study require registration with clinicaltrials.gov?

Yes

No

Subject Population(s)

Is this a study in which you will have interaction with individuals? NOTE: Please check "yes" if you need to report accrual goals for participant engagement.

Yes
 No

Accrual Goal: What is your total accrual goal?

525

Does this study target one gender or specific social/ethnic group(s)?

Yes
 No

Is the population being enrolled in this study at high risk for incarceration?

Yes
 No

Check all that apply (*Complete the appropriate supplemental information as applicable):

N/A
 Children/minors*
 Cognitively impaired - comatose/traumatized*
 Pregnant women/fetal tissue/placenta*
 Prisoners*

Recruitment

Describe the specific steps to be used to identify and/or contact prospective participants. (If applicable, also describe how you have access to lists of potential participants.)

Recruitment methods will include the use of interest cards, flyers and brochure, and referrals from healthcare providers and clinic staff, and in-person contact with patients in the clinic waiting room or at clinic and community events (see RCT Interest Cards, RCT Study Contact Cards, Recruitment Flyer with Tabs, and RCT Appointment Reminder Cards).

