We will use several items we will use as part of our retention efforts with participants over the course of the 15 month trial. These include a t-shirt, water bottle, magnet, and birthday card with the REACH logo, and a brief seasonal newsletter. KSP will offer the magnet and t-shirt or water bottle over the course of the study in person at an upcoming survey assessment. If the participant completes their surveys via e-mail or a mailed survey, KSP will mail the item with the study materials. Our team will mail the birthday card during the month of the participants' birthday which is signed by the team members. The newsletter will be mailed to participants or e-mailed for those with whom e-mail is the preferred contact method. The newsletters offer information about community events, updates from our team, and recipe ideas. We will also e-mail a brief seasonal newsletter to a liaison at our partnering clinics to share with staff. This newsletter will have updates from our team and study progress.

Describe how the selection of participants is equitable in relation to the research purpose and setting.

Given our study aims, this research does not require systematic procedures to ensure equitable selection. We will enroll adults with T2DM that are diverse with respect to age, gender, race, and ethnicity.

Please indicate whether you plan to enroll any of the populations indicated below:

- VU Medical Students/trainees
- Students
- Elderly/Aged - targeted
- Subordinates/Employees
- Females of childbearing potential
- Terminally ill participants
- Healthy Volunteers
- Other**
- Minorities

Please specify 'Other' populations:

Adults with T2DM and their adult family members

Please identify ALL applicable recruitment methods:

- N/A
- Flyers**
- Internet
- Letter**
- Departmental Research Boards,
- Mass E-mail Solicitation/Research Notifications Email Distribution List
- Newspaper
- Posters
- ResearchMatch (IRB 090207)
- Radio
- Telephone**
- Television
- Social Media
- Other**

Please describe other:

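### The HbA1c ≥8.5% subset was chosen from plots of the treatment effect and then tested on the same data, with no allowance for the selection and no direct test of what FAMS adds

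*SAP*

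**What the plan says.** The SAP section on REACH only and REACH+FAMS vs. control explains where the subset came from, citing the effects at months 3 and 6: "Data visualizations suggested effect modification by baseline HbA1c, in which those with a higher baseline HbA1c demonstrate a larger estimated effect". The data were then cut to baseline HbA1c of at least 8.5% (n=219), a value "which was the approximate mean value for baseline HbA1c". The stated reason is "To increase our power to detect any differential effects for REACH only as compared to REACH+FAMS".

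In this subset the GEE model was run "for REACH only vs. control and, separately for REACH+FAMS vs. control". Point estimates and 95% CIs come from least-squares regression with robust standard errors, for each outcome at each time point.

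The preceding SAP section sets the general rule: "Statistical significance for each hypothesis test was determined at the" 0.05 level. The subset is not exempted. That section also says all analyses compare any REACH with control "except for the subgroup analyses estimating additional effects of also receiving FAMS", so the subset results are the only arm-specific ones described. No interaction analysis, allowance for selection, exploratory label or estimate below 8.5% is given. The available protocol text does not mention this subgroup.

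**The concern.** Two things look wrong.

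First, the outcome data were used twice: once to find the patients in whom the effect looked larger, and again to test and estimate the effect in those patients. A subset kept because its observed effect was large carries the favourable chance error that made it look large. An ordinary p-value or CI ignores this, so benefit is overstated on average and false claims of benefit become more frequent.

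Second, the purpose is to compare REACH only with REACH+FAMS, but only two separate comparisons with control are described. One arm may be significant and the other not when the difference between them is no more than noise. What FAMS adds is therefore not tested.

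**Working it through.** The documents give no error rate, SD or power figure to reproduce. The size is therefore an illustration under stated assumptions.

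**Inputs**
- From the SAP: subset n=219; two intervention arms of equal size; alpha 0.05.
- From the protocol, Subject Population(s): the entry "Accrual Goal: What is your total accrual goal" is 525. The protocol lists its population as "Adults with T2DM and their adult family members", so 525 may include family members. N=525 is assumed, with 450 as a check.
- Assumed: no true effect anywhere; HbA1c is the plotted outcome, with SD 1.5 points (range 1.0–2.0); allocation control:REACH:REACH+FAMS of 1:1:1 or 2:1:1; one time point; selection on the pooled REACH effect, high stratum (H=219) against low stratum (L=525−219=306).

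**Formulas.** Let k = 1/(control share) + 1/(combined intervention share), which is 4.5 for 1:1:1 and 4 for 2:1:1.
- SD of the plotted gap: SD × √[k(1/H + 1/L)].
- Covariance of either arm's subset effect with the gap: SD² × k/H.
- Bias, given that the gap exceeds c standard errors: covariance ÷ gap SD × λ(c). Here λ(c) is the mean of a standard normal above c: λ(0)=0.798, λ(1)=1.525.
- SE of one arm vs control in the subset: SD × √(6/H) = 1.5 × √(6/219) = 0.248. The 6 applies to both allocations (3+3 and 2+4).

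**Numbers for SD 1.5, N=525**
- 1:1:1: covariance 2.25×4.5/219 = 0.0462; gap SD 1.5×√[4.5×(1/219+1/306)] = 0.282; ratio 0.164. Bias 0.164×0.798 = 0.13 (c=0) and 0.164×1.525 = 0.25 (c=1). Correlation of the arm's test statistic with the gap: 0.164/0.248 = 0.66.
- 2:1:1: covariance 2.25×4/219 = 0.0411; gap SD 0.266; ratio 0.155. Bias 0.12 and 0.24. Correlation 0.62.

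Error rates follow from the bivariate normal distribution with these correlations, and simulation of 1,000,000 null trials per setting agrees. All are conditional on the plot having shown the pattern.

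| Rule | Benefit-direction error per arm | Two-sided error per arm | Either arm | Bias (points, toward benefit) | CI coverage |
|---|---|---|---|---|---|
| Subset fixed in advance | 2.5% | 5% | 9% | 0 | 95% |
| (a) Subset looks better at all | 4.8–4.9% | 5% | 9% | 0.12–0.13 | 95% |
| (b) Gap at least 1 SE | 11–12% | 11–12% | 21% | 0.24–0.25 | 88–89% |

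**Sensitivity**
- Bias scales with the SD. For SD 1.0–2.0 it is 0.08–0.17 points in (a) and 0.16–0.33 in (b). Error rates do not depend on the SD.
- N=450: 10–11% per arm in (b).
- Selecting on the mean of the 3- and 6-month effects and testing at 6 months (within-patient correlation 0.6): 10–11% per arm and 19% for either arm in (b).
- Omnibus Wald test over 3–4 visits, as in the SAP, with the same selection: 5% in (a); about 8% per arm and 14–15% for either arm in (b).

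**What selection leaves intact.** The full-sample effect weights the strata by size. Its covariance with the gap is (SD² × k/N)(1−1) = 0, so full-sample arm-vs-control tests stay at 5% without bias. REACH+FAMS vs REACH only also stays at 5%, in the full sample and in the subset, because selection on the pooled effect moves both arms equally. An interaction test does not escape: under (b) its benefit-direction error is 0.025/0.159 = 16%.

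**Power.** At equal SD the subset's SE is √(525/219) = 1.55 times the full-sample SE (√(450/219) = 1.43 if N=450). The subset gains power only if the effect there exceeds the full-sample effect by more than that factor.

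Neither simulation models baseline adjustment or imputation.

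**The case against.** The SAP discloses how the subset arose, calls these subgroup analyses, and uses the approximate mean as the cut, with no sign of tuning. It says only that plots suggested a pattern. The weakest rule consistent with that is (a), where two-sided error does not move; the 1-SE threshold in (b) is an assumption. The SAP's own hypothesis test is the omnibus one, which is inflated less, and about 9% of its either-arm figure comes simply from running two tests. If effect modification is real and strong, the subset would nearly always be chosen and the selection bias would approach zero. The bias in points also assumes that HbA1c was plotted, whereas the protocol assigns FAMS mainly to family behaviours, self-efficacy, diet and exercise; outcomes weakly correlated with the plotted one are affected less. Finally, a direct arm contrast would be unbiased even within the subset.

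All of this stands as a limit on size, and (b) should be read as hypothetical. None of it removes the problem. Disclosure does not correct a CI, and bias toward benefit arises in the null case under either rule. That the direct contrast escapes the bias is a reason to report it, and the SAP does not.

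**Conclusion.** The concern holds and should be fixed. That the selection was data-driven and the inference unadjusted is clear from the text, and the missing direct contrast needs no assumption at all. The size is uncertain: under no true effect it runs from a directional shift with unchanged two-sided error (a) to roughly doubled per-arm error (b). It rests on the assumed SD, total N, allocation and selection rule. The damage is confined to the arm-specific subset results; the full-sample comparison of any REACH with control is untouched.

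**What to change.** - Report REACH only vs control, REACH+FAMS vs control and a direct REACH+FAMS vs REACH only contrast from the full-sample GEE as the arm-specific results.
- Examine effect modification in the full sample with a treatment by continuous baseline HbA1c interaction, giving effects and CIs at fixed baseline values.
- Label the interaction, those baseline-specific effects and any result at or above 8.5% as post hoc and exploratory. Show the estimate below 8.5% beside the subset result.
- Make no significance claim at 0.05 from these exploratory results.

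The cost is SAP wording, one three-arm model and one interaction model on data already held. The downside is that the subset result becomes hypothesis-generating only, and the full-sample arm effects may be smaller.

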This IRB application addresses the second of three aims for our overall research plan: to evaluate a mobile-phone delivered medication adherence intervention (called REACH; Rapid Education/Encouragement And Communications for Health) and test intervention effects on adherence and glycemic control among low income adults with type 2 diabetes mellitus (T2DM) receiving primary care at Federally Qualified Health Centers (FQHCs) or VUMC. In addition, family-focused components (called FAMS; Family-focused Add-on to Motivate Self-care) are integrated with the larger REACH intervention, and include diabetes coaching, goal-focused text messages delivered to the patient, and supplemental text messages delivered to an identified adult family member. We will evaluate the effects of the supplemental, family-focused intervention on family members' supportive and obstructive behaviors, patients' diabetes self-efficacy, and patients' adherence to diet and exercise. (Aim 1, to improve the content and functionality of an existing mobile phone-delivered medication adherence promotion intervention for consistency with the Information-Motivation-Behavioral skills model and clear health communication strategies, and test for usability and acceptability with patients, received approval [see IRB #140562] in April 2014.)

Expected duration of the study.

We expect to complete data collection by the end of 2019, but the study will remain open for analyses and manuscript writing/submissions for an additional five years.

The IRB needs to understand how this study adds to the knowledge on this topic in order to be able to judge the risks and benefits to the research participants.

BACKGROUND

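### FAMS is separated from REACH only in patients with baseline HbA1c of at least 8.5%, and the claimed power gain is unsupported for the outcomes named in the protocol's FAMS aim

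*SAP*

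**What the plan says.** The opening statement of purpose in the protocol undertakes to evaluate the effects of the family-focused supplement "on family members' supportive and obstructive behaviors, patients' diabetes self-efficacy, and patients' adherence to diet and exercise". It does not limit that aim to patients with poor glycaemic control.

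The first section of the SAP pools the two intervention arms. All analyses compare the pooled arms "to control except for the subgroup analyses estimating additional effects of also receiving FAMS".

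Those subgroup analyses are in the SAP section on REACH only and REACH+FAMS vs. Control. Its starting point is plots suggesting effect modification, in which "those with a higher baseline HbA1c demonstrate a larger estimated effect at 3 and 6 months than those with a lower baseline HbA1c". The stated purpose follows: "To increase our power to detect any differential effects for REACH only as compared to REACH+FAMS, we conducted analyses with a subset of data". The subset is "participants with a baseline HbA1c $\geq 8.5\%$ (69 mmol/mol; $n=219$), which was the approximate mean value for baseline HbA1c".

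The models are then described: "With this reduced dataset, we conducted the same GEE model described above for REACH only vs. control and, separately for REACH+FAMS vs. control". Least-squares estimates with robust standard errors are given for each outcome at each visit. The SAP lists no outcomes, does not name the outcome that was plotted, and does not give the total number analysed.

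**The concern.** A comparison that isolates FAMS exists only in the subset, so the protocol's FAMS aim has no full-sample analysis. The restriction is justified by power, but removing patients raises power only where the effect among those who remain is enough larger to offset the lost precision. The SAP's one supporting observation is a pattern in plots of an unnamed outcome. It offers nothing of the kind for family behaviour, self-efficacy, diet or exercise. The models adjust for the baseline value of the outcome being analysed, so for these outcomes baseline HbA1c acts purely as a filter.

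At stake is how the FAMS result can be read. A null finding on self-efficacy or family behaviour could reflect the smaller sample rather than an ineffective supplement. A positive finding would describe patients at or above roughly the mean HbA1c, not the randomised FAMS arm.

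**Working it through.** **Inputs.**
- Subset size: 219 (SAP).
- Total N: not given. The protocol entry "Accrual Goal: What is your total accrual goal" is answered 525. That is a target, and it may include family members, because the protocol's recruitment section describes the enrolled populations as adults with T2DM and their adult family members. I therefore treat patient N as an assumption and vary it.
- Alpha: 0.05 (SAP), taken as two-sided in keeping with the 95% CIs.
- Allocation: the intervention group is split in half (SAP). The control share is not stated, so 1:1:1 and 2:1:1 are both tried.

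The figure of 219 cannot be reproduced, since neither the achieved N nor the baseline HbA1c distribution is reported. The documents contain no power calculation to check.

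**Step 1: loss of precision.** With the same SD and arm shares in the subset as in the full sample:
- share dropped = 1 − 219/N
- SE ratio = sqrt(N/219)
- power in the subset for an effect with 80% power in the full sample = Φ((1.960 + 0.842)/sqrt(N/219) − 1.960)

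For N = 525: 1 − 219/525 = 0.583; sqrt(525/219) = 1.548; Φ(2.802/1.548 − 1.960) = Φ(−0.15) = 0.44.

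| Assumed patient N | Dropped | SE ratio | Power in subset (full sample 80%) |
|---|---|---|---|
| 525 | 58% | 1.55 | 44% |
| 480 | 54% | 1.48 | 47% |
| 450 | 51% | 1.43 | 50% |
| 438 | 50% | 1.41 | 51% |
| 400 | 45% | 1.35 | 54% |

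The power column assumes that the effect is the same in the subset as in the full sample. Since 2 × 219 = 438, more than half the patients are dropped only if N exceeds 438.

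**Step 2: break-even.** At equal SD, power is unchanged when the subset effect is sqrt(N/219) times the full-sample effect: 1.55 times at N = 525, 1.43 at 450, 1.35 at 400. The full-sample effect is itself an average over both sides of the cut-off. With p = 219/N, setting p·d_high + (1 − p)·d_low = sqrt(p)·d_high gives d_high/d_low = 1 + 1/sqrt(p) = 1 + sqrt(N/219). At N = 525 the effect above the cut-off would have to be about 2.55 times the effect below it; at 400, about 2.35 times.

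**Step 3: detectable difference, 80% power, N = 525 assumed.** For REACH+FAMS against control the difference in SD units is 2.802 × sqrt(1/n_control + 1/n_FAMS).
- Full sample, 1:1:1: 2.802 × sqrt(1/175 + 1/175) = 0.30.
- Subset, 1:1:1: 2.802 × sqrt(1/73 + 1/73) = 0.46.
- Under 2:1:1 the results are the same, because 1/(N/2) + 1/(N/4) = 6/N, as under 1:1:1.

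For a direct REACH+FAMS against REACH-only contrast, the values are 0.30 (full) and 0.46 (subset) under 1:1:1, and 0.35 and 0.54 under 2:1:1.

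**The case against.** Four objections carry weight, and each limits what can be said.

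- A reader might infer that effect modification was seen only for HbA1c as an outcome. The SAP names HbA1c as the modifier but not the outcome plotted. That it was HbA1c is plausible, not stated.
- A reader might infer that the restriction certainly discards most of the sample. That rests on an accrual goal that may count family members, and it fails if 438 or fewer patients were analysed.
- A reader might infer that the restriction defeats its own purpose. That needs roughly equal effects on both sides of the cut-off, which the documents do not show. The protocol background links adherence and family behaviour to glycaemic control, so larger effects above 8.5% cannot be ruled out. If they exceeded the break-even ratio, the subset would indeed gain power.
- A reader might infer that the protocol's FAMS outcomes were definitely analysed in the subset. The SAP says only that each outcome was, and gives no list.

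The SAP also calls these analyses subgroup analyses and discloses that the plots prompted them, and the all-patient comparison of any REACH with control is untouched.

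The core point survives. The SAP invokes power to justify dropping patients, so it needs to show the pattern for the outcomes concerned. The last objection does not rescue the plan: if the protocol's FAMS outcomes are not covered, the SAP has no analysis isolating FAMS on them at all.

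**Conclusion.** The concern holds in this form: the only analysis that isolates FAMS is confined to a subset chosen after looking at the data, and the power gain claimed for it is unsupported for the family-behaviour, self-efficacy, diet and exercise outcomes. This is absence of support, not proof of a loss.

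If the effect in the subset equals the full-sample effect at equal SD, 80% power falls to between 44% (N = 525) and 54% (N = 400). The detectable difference for REACH+FAMS against control rises from 0.30 to 0.46 SD at N = 525. The exact size depends on the unreported patient N. The conclusion does not depend on whether more than half the sample is dropped.

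**What to change.** 1. List the FAMS outcomes in the SAP: supportive and obstructive family behaviours, diabetes self-efficacy, diet and exercise. State the number of patients randomised and analysed. State whose report measures family behaviours, since only the FAMS arm invites family members and the comparison needs a measure taken in every arm.
2. Fit the existing GEE and per-visit least-squares models to all randomised patients with a three-level arm term, for those outcomes and for HbA1c. The same fit gives the direct REACH+FAMS minus REACH-only difference, which is the comparison the stated purpose refers to.
3. Keep the subset at or above 8.5% only as an HbA1c analysis labelled post hoc and exploratory. Name the outcome or outcomes in which effect modification was seen, and limit the power rationale to those.

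The cost is SAP wording and a re-run of existing models on data already collected. No new patients or procedures are needed.
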